To address the need for programs to reduce financial strain among Latino caregivers, we developed the Confidently Navigating Financial Decisions and Enhancing Financial Wellbeing in Dementia Caregiving (CONFIDENCE) program with support from AARP Foundation from 2020 to 2023. The original version of CONFIDENCE includes a 5-week, group-based psychoeducational intervention delivered by Zoom. Most data for the evaluation of the CONFIDENCE original program have been collected. Initial findings indicate high satisfaction with the program among participants (100% “Agree” or “Strongly Agree” they would recommend the program to other caregivers), but also lower-than-anticipated uptake and adherence. For example, only 51% of caregivers registering for CONFIDENCE at the USC Family Caregiver Support Center attended at least one session. Of those who attended at least one session, average attendance was 3.1 out of 5 sessions. These findings suggest high acceptability but limited feasibility.

The second version of CONFIDENCE aims to build on lessons learned from the original CONFIDENCE program with the goal of improving program feasibility prior to testing the program’s efficacy. To improve uptake and adherence, we have shortened the number of group-based Zoom discussion sessions from 5 to 4 to reduce the time required to participate. Content covered in the sessions removed from the core program will be delivered by asynchronous, technology-driven means. Participating caregivers will have a chance to decide which topics to focus on based on their current needs and will receive informational text messages covering these topics. Caregivers will also have access to a conversational AI assistant (“Keiko”) that will draw from hand-picked and trusted resources to devise answers to questions caregivers may have about topics such as how to find reduced-cost home modifications, how to prepare for retirement, and how to prevent financial scams. To support learning between discussion sessions, NeuViCare also will host a moderated community forum where caregivers can connect with other participating caregivers .

*Please add relevant references at the end of the protocol, not at the end of this section.*

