## 4.0 Inclusion and Exclusion Criteria

**Directions: Describe how individuals will be screened for eligibility.**

Participants will be asked to either complete an online self-administered survey to determine their eligibility, or to complete eligibility questions by telephone.

**Using the tables below, describe the inclusion and exclusion criteria that will define who will be included and excluded in your final study sample.**

Inclusion	
1.	Age range: from 18 to not upper limit
2.	Has been at least 6 months since the care recipient began to experience dementia symptoms
3.	Person living with dementia meets stage 4 to 6 criteria on Global Deterioration Scale according to family caregiver
4.	Latino/Hispanic ethnicity

Exclusion	
1.	Individuals who plan to place their family member in a nursing home in the next 3 months
2.	Unreliable access to internet, tablet or smart phone, and email
3.	Does not agree to participate in at least 3 of the 4 group sessions and/or register for the NeuViCare app
4.	Unable to read and speak in English or Spanish

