**Attendance.** Attendance to each session will be recorded by facilitators and shared with Case Western using a Box folder. The average number of sessions attended by participants and the standard deviation will be reported and compared between the English and the Spanish sessions. Another comparison, in the form of percentage based on the different number of possible sessions to attend, will be made on attendance between CONFIDENCE vs CONFIDENCE.

**Participant safety monitoring.** *Confidentiality.* All survey data will be de-identified and only the PI will have access to the identifier information. NeuViCare user data will be tracked using an email address and phone number. Only the PI will have access to the study key that will allow link study data to contact information, and will not share this with other study team members to prevent breach of privacy. *Transient emotional distress.* If caregivers experience emotional distress while interacting with a study team member, they will be referred to resources of self-care, community support and the Alzheimer's Association 24/7 Helpline. **Adverse events.** All suspected study adverse events will be reported using a standardized form in REDCap. These will be tracked and monitored by the PI. All study team members will be trained to identify on risk management protocols, such as when to immediately contact the PI about a suspected adverse event. See the Adverse Event Form.

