**Satisfaction surveys.** To analyze Likert responses to satisfaction surveys, a percentage for each response will be provided. Each item will be compared to items collected for the initial CONFIDENCE study, as well as scores for items of CONFIDENCE between Spanish and English intervention.

**Attendance.** We will report the average number of sessions attended (range 0 to 4) and the standard deviation. Comparison on the number of sessions attended will be compared between the English and the Spanish sessions as well as between the earlier and current version of CONFIDENCE in the form of percentages to allow us to draw preliminary comparisons, given the different number of possible sessions to attend (3 vs. 5). The average number of sessions will be calculated both with and without accounting for make-up sessions. (i.e., giving credit for attendance in Session 1 if the caregiver attended the makeup session for this lesson.)

**App Utilization.** Usage data from NeuViCare™ Care and Resources Advisors will be reported in aggregate Individual-level data will be collected on the average number of text received, average interactions on the Community Hub, and average number of practice activities completed on NeuViCare.

**Fidelity.** Fidelity reports will be evaluated using total scores averaged across all CONFIDENCE sessions observed. Sub scores will be reported for adherence to the facilitator guide, participant experience, and quality of delivery. These will be reported separately for English and Spanish participants by using a percentage, as well as means and standards of deviation, to examine variability.

**Qualitative interviews.** Qualitative interviews will be transcribed verbatim, and for the ones conducted in Spanish, they will be previously translated. Transcription and translation of interviews conducted in Spanish will be by ASTA-USA. English Transcriptions will be done by GMR. A preliminary code book will be developed by at least two research members and will be refined prior to applying codes to the remaining interviews. At least two coders will analyze each transcript independently and will meet to compare the codes. The second round of coding will be conducted to integrate new codes if needed.

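### The attendance comparison with the original programme states 3 possible sessions for a 4-session programme, leaves its population and comparator unspecified, and has no uptake figure

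*Combined protocol and SAP*

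**What the plan says.** Section 3.0 (Background) reports two results for the original five-session programme. On uptake, "only 51% of caregivers registering for CONFIDENCE at the USC Family Caregiver Support Center attended at least one session". On adherence, "Of those who attended at least one session, average attendance was 3.1 out of 5 sessions". From these it concludes that feasibility was limited, and it gives the reason for the redesign: "To improve uptake and adherence, we have shortened the number of group-based Zoom discussion sessions from 5 to 4".

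Section 17.0 (Attendance) sets out the analysis: "We will report the average number of sessions attended (range 0 to 4) and the standard deviation". The earlier and current versions are then to be compared "in the form of percentages to allow us to draw preliminary comparisons, given the different number of possible sessions to attend (3 vs. 5"). The mean is to be calculated both with and without credit for make-up sessions.

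Section 12.0 (Attendance) has parallel text. "The average number of sessions attended by participants and the standard deviation will be reported", and a comparison "in the form of percentage based on the different number of possible sessions to attend, will be made on attendance between CONFIDENCE vs CONFIDENCE". The same name stands on both sides of that comparison, and no population is defined.

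One exclusion criterion in Section 4.0 bears on attendance: "Does not agree to participate in at least 3 of the 4 group sessions and/or register for the NeuViCare app".

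**The concern.** There are three separate problems.

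- **Session count.** The pair 3 and 5 stands in the sentence that justifies the percentages, so it reads as the pair of divisors. No session total elsewhere in the document is 3. The number does occur in Section 4.0, as the minimum a caregiver must agree to attend, so an analyst could take it for a deliberate choice.
- **Population and comparator.** Converting to percentages adjusts for the number of sessions offered, but not for which people are counted. Neither attendance paragraph says whether the average covers enrolled participants, everyone who attended, or all registrants. Neither names the original summary to be used.
- **Uptake.** Section 3.0 rests its judgement of limited feasibility on uptake as well as adherence, and the redesign targets both. Section 17.0 plans no uptake figure.

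Feasibility is a stated objective (Section 2.0), and improving it before efficacy testing is the stated goal of version 2 (Section 3.0). As written, the plan could produce a percentage that looks better or worse than the original for reasons unrelated to adherence, and it would leave the uptake question unanswered.

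**Working it through.** **Inputs from the documents.** Original uptake 51% of registrants; original mean 3.1 of 5 among those attending at least once (both Section 3.0). Version 2 sessions: 4 (Sections 3.0, 4.0, 8.0 and 12.0, and the range in Section 17.0). Target enrolment 42 (Section 5.0). The number of registrants and the share who never attend version 2 are not given, so the values used for them below are assumptions.

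**1. The stated session count.** Setting 3 against every session total in the document gives no match; all the others are 4. The figure cannot be reproduced.

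**2. Effect of the divisor.**
- Original adherence among attenders: 3.1/5 = 62.0%.
- Equal adherence over four sessions: 0.62 × 4 = 2.48 sessions.
- The same result divided by 3: 2.48/3 = 82.7%.
- Full attendance divided by 3: 4/3 = 133%.
- A real fall to 1.86 of 4 (1.86/4 = 46.5%) would still read 1.86/3 = 62%.

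**3. Effect of including never-attenders, dividing by 4.** If a share z of those averaged never attend, the percentage is 0.62 × (1 − z).
- z = 10% (assumed): 0.62 × 0.90 = 55.8%.
- z = 20% (assumed): 0.62 × 0.80 = 49.6%.

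With 42 people averaged, a true 70% among attenders reads 0.70 × 38/42 = 63.3% if 4 never attend, and 0.70 × 37/42 = 61.7% if 5 never attend. Whether a gain of that size is hidden depends on a count that the plan does not forecast.

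**4. The original over all registrants.** 0.51 × 3.1 = 1.58 sessions, and 1.58/5 = 31.6%. This derived figure is the like-for-like comparator for a zero-inclusive version 2 mean taken over all registrants. The 62% is not.

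**5. Precision of an uptake figure.** Wilson 95% intervals for an observed uptake near 51%, with assumed registrant numbers:
- 31 of 60: 39.3% to 63.8%.
- 76 of 150: 42.7% to 58.6%.

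An uptake percentage without its interval would look more precise than it is.

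**6. Whether the data exist.** Section 16.0 downloads Eventbrite data on registrants whether or not they join the study, and says that such data were also collected in the previous study. Section 12.0 has facilitators record attendance at each session. Section 15.0 lists attendance, but does not say that it covers people who are not enrolled.

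**The case against.** The best defence is that the documents do not commit the team to a mismatched comparison. A reader might infer that version 2's zero-inclusive mean will be set directly against 3.1 of 5. The text does not say so. Section 17.0 names no original summary, and the range of 0 to 4 may only give the possible values of the variable. Section 3.0 presents 3.1 as an early result of the original evaluation, and the team may be able to re-tabulate the original on another base. This part of the defence stands: the fault is an unspecified population and comparator, not a demonstrated mismatch.

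Other points also carry weight.

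- The 3 is probably a slip. The right maximum stands in the same paragraph, and a result above 100% would probably expose the error.
- The never-attender shares are assumptions, and the masking example with 42 people turns on a single person.
- The plan already calls the comparison preliminary, attaches no test or decision rule to it, and handles make-up sessions both ways. Nothing more is needed on those points.
- Attendance is not among the outcome measures named in Section 17.0.

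The defence does not remove the wrong session count or the missing uptake figure. A descriptive percentage still needs a stated divisor and a stated population, and these are better fixed before the results are seen.

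**Conclusion.** The point holds and should be fixed. The session count is wrong as written, and Section 17.0 has no counterpart to the 51% uptake; confidence on both is high. Taken literally, the count would show an unchanged 62% as 82.7%. Confidence on the denominator is moderate: the plan does not define it, and a mean that included never-attenders would not be comparable with 62%. The 55.8% rests on an assumed 10% who never attend and on unchanged adherence among attenders. It is an illustration, not a forecast.

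A reader might also conclude that the comparison is biased in a known direction. The documents do not support that. Counting zeros lowers the version 2 percentage and dividing by 3 raises it. The agreement required at enrolment may raise it too if only enrolled people are averaged, but the documents do not say whether the original study had such a rule. The net direction is not established.

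**What to change.** In Section 17.0 (Attendance), and to match in Section 12.0:

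1. Reconcile the stated pair of session counts with the four sessions given elsewhere, and use 4 as the divisor for version 2.
2. Report uptake, defined as those attending at least one session divided by all registrants, with a 95% confidence interval, beside 51%. Aggregate counts are enough. Note the differences in who could register (version 2 is offered nationally, while the original figure is for registrants at the USC centre) and any screening between registration and attendance.
3. Report the mean percentage of four sessions among those attending at least one, beside 62%. Show any zero-inclusive mean separately, over all registrants, beside the derived 31.6%.
4. State whose attendance is averaged, and show enrolled participants separately, because enrolment depends on the agreement described in Section 4.0.

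The cost is a few sentences and slightly more tabulation. The all-registrant figures will probably look less favourable. If attendance of non-enrolled people is to be linked individually, IRB review may be needed. That choice must be made early, because Section 18.0 (Confidentiality of Data) provides for deleting identifying Eventbrite columns before saving and for deleting the study key.

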## 12.0 Study Design/Procedures

### Directions:

- 1) **Describe the overall study design (e.g.: single visit, single-blind, double-blind, non-randomized, randomized, blood draw, investigational drug, device etc.).**
- 2) **Provide a description of all study-related research procedures being performed, including the length of time involved.**
- 3) **Include procedures being performed to monitor research participants for safety or minimize risks.**
- 4) **Describe the source records including medical or educational records, which will be used to collect data about subjects.**
- 5) **Include a description of any device being used to collect data (e.g., eye tracker, step counter). If the device itself is being studied, include additional information in Section 29.**

**Overall design.** A single-arm pre- and post-test clinical trial of the CONFIDENCE intervention will be conducted. This study builds on the original CONFIDENCE study (STUDY20221010), but with a modified version of the intervention and minor updates in data collection protocols to reduce participant burden. Participation will be offered to any caregiver of persons living with dementia nationally who register for the program via the USC Family Caregiver Support Center (USC FCSC) Eventbrite. Study participation is optional. CONFIDENCE will be delivered in English and Spanish, and participants may participate in the study in either language.

**Intervention** The intervention includes participation in four, 1.5 hour group discussion sessions delivered by Family Consultants from the USC Family Caregiver Support Center. Zoom sessions will be attended by other caregivers and will feature vignette-style videos featuring family caregivers as well as peer-learning activities. Between the sessions, caregivers will receive text messages from NeuViCare™ with informational tips and reminders to complete practice exercises. They may also choose to interact with Keiko, the apps conversational AI assistant that generates responses to questions based on sources selected or created by the study team. Caregivers can also participant in a monitored community forum, wherein they will be able to communicate with other caregivers in the program. Participants will be sent instructions on how to register for the NeuViCare App, and will have a dedicated “NeuViCare champion” at the USC FCSC who they can turn to if they need additional support. Total time for intervention participation in 8 to 10 hours over 4 weeks.

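### Expressing attendance as a percentage does not by itself make the five-session and four-session versions comparable; the contrast can be distorted in either direction, and upward if attendance declines over sessions

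*Combined protocol and SAP*

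**What the plan says.** Section 3.0 (Background) gives the original programme's adherence: "Of those who attended at least one session, average attendance was 3.1 out of 5 sessions". It also reports that "only 51% of caregivers registering for CONFIDENCE at the USC Family Caregiver Support Center attended at least one session". In response, with the stated aim of better uptake and adherence, "we have shortened the number of group-based Zoom discussion sessions from 5 to 4 to reduce the time required to participate". Section 12.0 describes the current intervention as "four, 1.5 hour group discussion sessions".

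The comparison with the original appears twice. The Attendance paragraph of section 12.0 makes it "in the form of percentage based on the different number of possible sessions to attend". The Attendance paragraph of section 17.0 makes it "in the form of percentages to allow us to draw preliminary comparisons, given the different number of possible sessions to attend". Neither paragraph plans a display by session, a restriction to the sessions common to both versions, or a measure of retention from one session to the next.

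On make-up sessions, section 17.0 says: "The average number of sessions will be calculated both with and without accounting for make-up sessions". It does not say which of the two averages is set against the original, and section 3.0 does not say whether the original's 3.1 includes make-ups.

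**The concern.** Dividing by the number of possible sessions removes programme length only if average attendance is flat across sessions. If later sessions are less well attended, a programme with one session fewer shows a higher percentage even when caregivers behave identically at each session they are offered. If later sessions are better attended, the reverse happens.

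The change made to improve adherence, a shorter programme, is thus also a change that can move the measure. Feasibility is part of the stated objective in section 2.0, and low attendance is one reason section 3.0 gives for calling the original's feasibility limited. A reader who sees a percentage above 62% may take it as evidence that attendance improved when some or all of the difference is arithmetic. A true improvement could also be hidden. A larger sample would not remove either effect.

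**Working it through.** **Inputs.** Original mean attendance among those attending at least one session: 3.1 of 5 (section 3.0). Sessions: 5 in the original (section 3.0) and 4 now (sections 3.0, 4.0 and 12.0, and the 0-to-4 range in section 17.0). The share of original attenders present at session 5, f5, is not in the documents and is an assumption throughout.

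**The plan's own figure.** 3.1/5 = 62.0%. Allowing for rounding of 3.1 (3.05 to 3.15), this is 61% to 63%. The 3.1 is an observed mean and cannot be re-derived without the session data.

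**Hold behaviour fixed and drop the fifth position.** The mean over the first four sessions is (3.1 - f5)/4. The shift from 62% is (3.1 - f5)/4 - 3.1/5 = (0.62 - f5)/4, so its sign depends only on whether f5 is below or above 62%.

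| Assumed f5 | Mean over first four sessions | Shift in points | Mean sessions attended (3.1 - f5) |
|---|---|---|---|
| 0% (limit) | 77.5% | +15.5 | 3.10 |
| 30% | 70.0% | +8.0 | 2.80 |
| 40% | 67.5% | +5.5 | 2.70 |
| 50% | 65.0% | +3.0 | 2.60 |
| 62% | 62.0% | 0 | 2.48 |
| 80% | 57.5% | -4.5 | 2.30 |
| 100% (limit) | 52.5% | -9.5 | 2.10 |

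**Check with whole attendance curves**, each an assumption and each fixed to average 3.1 of 5:

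- Constant retention r with 1 + r + r² + r³ + r⁴ = 3.1 gives r = 0.758. The first four sessions sum to 2.77, and 2.77/4 = 69.2% (68.3% to 70.1% for a mean of 3.05 to 3.15).
- Linear decline from 100% (100, 81, 62, 43, 24): 286/4 = 71.5%.
- Linear decline from 70% (70, 66, 62, 58, 54): 256/4 = 64.0%.
- One drop after session 1, then flat at (3.1 - 1)/4 = 52.5%: (1 + 3 × 0.525)/4 = 64.4%.
- Flat: 62.0%. If attendance is flat and independent between sessions and only those attending at least once are counted: 62.9%.
- Linear rise from 50% (50, 56, 62, 68, 74): 236/4 = 59.0%. From 40% (40, 51, 62, 73, 84): 226/4 = 56.5%.

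The declining curves tried give 64.0% to 71.5%, about 2 to 10 points above 62%. Under the same curves the mean number of sessions attended falls from 3.1 to about 2.6 to 2.9.

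**Denominator population.** The 62% counts only people who attended at least once, whereas the current measure runs from 0. If all registrants are counted, the original figure is 0.51 × 62% = 31.6%. The two sides therefore need one population before any percentages are compared.

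**A discrepancy in the same sentence.** The parenthesis in section 17.0 gives the possible sessions as 3 against 5, while the other places listed above give 4. These passages must be reconciled. The point here remains when 4 is used, as it is in this working.

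**The case against.** The strongest reply is that decline is not documented. A mean of 3.1 of 5 is compatible with falling, flat or rising attendance; flat attendance makes the effect zero or below 1 point, and rising attendance reverses it. This stands. A reader might infer that the current version's percentage is bound to be inflated, by 3 to 8 points for example. That figure holds only if f5 is assumed to lie between 50% and 30%, and the documents support neither the direction nor the size.

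Second, the percentage of planned sessions attended is a legitimate adherence measure. The programme was shortened so that caregivers could complete more of it, and a higher share completed is partly a real feature of the shorter programme. This also stands, and it is why the percentage should be kept. It answers a different question from whether caregivers came more reliably at each session.

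Third, the contrast is descriptive and labelled preliminary, with no test, threshold or decision rule attached. A reader might infer that it decides whether the shortening worked. The plan does not say so; it also reports satisfaction, app use, fidelity and interviews, and its primary outcomes are resourcefulness and self-efficacy. That limits the weight of the point. But calling a comparison preliminary warns of imprecision, not of a possible systematic shift.

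Fourth, the plan already reports the mean number of sessions attended, which under the declining curves would fall below 3.1 and alert a careful reader. This is a partial safeguard, but the mean is not tied to the cross-version comparison.

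Lastly, section 3.0 does not say which session was removed, and a mean of 3.1 can be computed from per-person totals, so per-session records may not be held. Both are real limits on the remedy.

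**Conclusion.** The point holds in conditional form. The percentage of possible sessions is the plan's only adjustment for programme length, and it is neutral only if attendance is flat. With behaviour at each position unchanged, the original's 62% could correspond to anything from 52.5% to 77.5% over its first four sessions. It rises if session 5 attendance was below 62% and falls if it was above. A higher percentage in the four-session version cannot, alone, be read as better session-by-session adherence. The calculation assumes that the fifth position is the one dropped and that programme length does not alter behaviour at the others.

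The unspecified make-up rule is a smaller gap in the same contrast. Both averages will be reported, so nothing is hidden, but the one used against the original is not named.

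This should be changed because the addition is cheap and shows whether an apparent gain goes beyond arithmetic. It does not affect the primary outcomes.

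**What to change.** In the Attendance paragraphs of sections 12.0 and 17.0, keep the percentage of planned sessions, label it descriptive, and add beside it:

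- the percentage present at each session position in each version;
- the mean over positions 1 to 4 in both versions, with the original's session 5 shown separately;
- the mean number of sessions attended in each version.

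State one denominator population for both sides (all registrants, or those attending at least once) and, where the original study's records allow, apply the same make-up rule to both and name it. Base any statement about improved adherence on these figures together.

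The cost is a few lines of text and no new data collection in this study, since section 12.0 already records attendance at each session. The remedy does need the original study's per-session attendance records. Because the documents do not say which session was removed, the comparison is by position and not by content. If the records are not available, state in the plan and the report that the percentage contrast cannot separate programme length from attendance behaviour.

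### The cross-version attendance comparison cites 3 possible sessions for CONFIDENCE 2, which has 4 everywhere else; dividing by 3 would inflate attendance percentages by a third

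*Combined protocol and SAP*

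**What the plan says.** Section 17.0 (Data Analysis Plan), Attendance, sets out the attendance summary: "We will report the average number of sessions attended (range 0 to 4) and the standard deviation". It then plans two comparisons, English against Spanish sessions and the earlier against the current version of the programme. The second is made in percentages, "given the different number of possible sessions to attend (3 vs. 5"). The paragraph also reports the average with and without make-up sessions, the former by "giving credit for attendance in Session 1 if the caregiver attended the makeup session for this lesson".

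Section 12.0, Attendance, describes the same cross-version comparison as a "percentage based on the different number of possible sessions to attend, will be made on attendance between CONFIDENCE vs CONFIDENCE". It gives no session counts there and uses one name for both versions.

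Elsewhere the current programme has four group sessions:

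- Section 3.0 (Background): "we have shortened the number of group-based Zoom discussion sessions from 5 to 4 to reduce the time required to participate".
- Section 4.0, third exclusion criterion: "Does not agree to participate in at least 3 of the 4 group sessions".
- Section 8.0 (Recruitment Methods) lists the cut from 5 to 4 live sessions among the reasons to expect better enrolment.
- Section 12.0, Intervention, specifies four sessions of 1.5 hours, and the Qualitative interviews paragraph uses attendance at all four as its example of engagement.

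**The concern.** A participant whose attendance can run from 0 to 4 cannot have had only 3 sessions available, so the Attendance paragraph of section 17.0 contradicts itself as well as the rest of the protocol. The figure matters because the number of possible sessions is the denominator of the planned percentage.

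Feasibility is one of the stated objectives in section 2.0. Section 3.0 judges the original programme's feasibility to be limited because uptake and adherence were low, and says the programme was shortened to improve both. The percentage comparison is the plan's only stated method for comparing attendance across versions. A denominator that is too small would make CONFIDENCE 2 look better attended than it was, and could show an improvement where there was none.

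**Working it through.** **Inputs**

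- Possible sessions as printed in the cross-version comparison (17.0, Attendance): 3 and 5.
- Possible sessions in the current version (3.0, 4.0, 8.0, 12.0, and the 0-to-4 range in 17.0): 4.
- Possible sessions in the original version (3.0, 8.0): 5.
- Original-version attendance (3.0): "Of those who attended at least one session, average attendance was 3.1 out of 5 sessions".

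**Can the printed figure be reproduced?** The 5 can. The 3 cannot. Two possible sources were tried:

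1. Section 4.0 contains a 3, but as the minimum a participant agrees to attend out of 4. It is not the number possible.
2. The make-up rule credits a lesson that was missed and then made up. It changes the numerator and leaves the number of possible sessions at 4.

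No section describes a three-session programme.

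**Effect of dividing by 3.** Let *m* be the mean number of sessions attended. The percentage is *m*/4 under the described design and *m*/3 under the printed figure. The ratio is (*m*/3)/(*m*/4) = 4/3 = 1.333 for any non-zero *m*; zero stays zero.

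| Sessions attended | Out of 4 | Out of 3 |
|---|---|---|
| 1 | 25.0% | 33.3% |
| 2 | 50.0% | 66.7% |
| 2.48 | 62.0% | 82.7% |
| 3 | 75.0% | 100.0% |
| 4 | 100.0% | 133.3% |

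**Illustration against the original programme.** The plan does not name the comparator value, so this uses the section 3.0 figure: 3.1/5 = 62%.

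- Dividing by 3, CONFIDENCE 2 would equal 62% at 0.62 × 3 = 1.86 sessions, which is 1.86/4 = 46.5% of the sessions on offer.
- Dividing by 4, it equals 62% at 0.62 × 4 = 2.48 sessions.
- A mean above 1.86 and below 2.48 would therefore read as an improvement when attendance had fallen. At exactly 2.48 the two versions are tied, but the comparison would read 82.7% against 62%.
- At a mean of 3.0 the direction would be right but the size wrong: 100 − 62 = 38 points instead of 75 − 62 = 13 points.

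**The case against.** The best case for leaving this alone is that it is a slip nobody would act on. The parenthesis explains why percentages are used; it does not formally set a denominator. Section 12.0 bases the percentage on the number of possible sessions, and its Intervention paragraph gives that number as four, so the two together already yield 4. The sentence in section 17.0 also names the earlier version before the current one, so on a literal reading the 3 would belong to the original programme. An analyst has to consult other sections to match figures to versions, and would find the 4 while doing so. Full attenders scoring 133% would be a further warning.

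Much of this stands, and it keeps the point minor. It does not remove the contradiction: the parenthesis is the only place in the analysis plan that gives the counts for this comparison, and one of them is wrong. The over-100% warning is also only partial. A group mean exceeds 100% only above 3.0 sessions, and a mean of 2.48 would read as a plausible 82.7%.

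A second objection is that 62% is a weak comparator. It covers only those who attended at least one session, whereas the CONFIDENCE 2 range starts at 0, and section 3.0 says of the original evaluation that "Most data for the evaluation of the CONFIDENCE original program have been collected", so the figure is interim. This is fair. The 1.86-to-2.48 band and the 38-against-13 contrast show how the error works and are not forecasts. The 4/3 factor does not depend on that comparator.

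**Conclusion.** The concern holds. The figure of 3 possible sessions is wrong as written: it conflicts with the 0-to-4 range in its own paragraph and with every other description of the programme. If it were used, all non-zero CONFIDENCE 2 percentages in the cross-version comparison would be overstated by a factor of exactly 4/3, in favour of the new version.

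Severity is minor. The distortion depends on 3 actually being used as the denominator for the current version. The comparison is descriptive and labelled preliminary, attendance is not among the outcome measures listed in section 17.0, and no test or sample size depends on it. The mean, the standard deviation and the English–Spanish comparison of session counts are unaffected.

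**What to change.** In section 17.0, Attendance, replace the counts in the parenthesis with 4 for CONFIDENCE 2 versus 5 for the original programme, so that the analysis denominator agrees with the design described in the other sections. In section 12.0, Attendance, name the two versions being compared and give the same counts, 4 and 5.

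The cost is a one-line correction in section 17.0 and matching wording in section 12.0. No new data are needed. Making the change before analysis removes any doubt about which denominator was planned.
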